**12.5.5 Assessing the Effects of EIMG**

We will use episode of care level data generated using the quasi-experimental stepped wedge design to estimate the relationship between EIMG referral and study outcomes. Outcomes will include:

*Episode Healthcare Costs* – the price-weighted sum of all healthcare resources used by patient “i” during the episode of care

*Episode-Specific Health Outcomes* - Change in health outcomes (blood pressure; body weight; hemoglobin A1c; full lipid profile and physical activity for patient “i”) between the index visit and the first provider visit in the episode in the Outcome Period (Figure 6) in which this information is collected.

We will initially regress whether patients in an episode were referred to EIMG on variables representing whether the patient’s clinic had received standardized EIMG training, patient clinical and demographic characteristics, time trends, and clinic specific fixed effects represented by:

$$(2) \quad E_{ijk} = \beta_0 + \beta_1 \cdot X_{ijk} + \beta_2 \cdot L_j + \beta_3 \cdot M_k + \beta_4 \cdot C_{ijk} + \omega_j + u_k + \epsilon_{ijk}, \text{ where}$$

$E_{ijk}$  equals 1 if patient “i” in the episode at clinic “j” in the “k-th” month after study initiation was referred to EIMG, 0 otherwise;  $X_{ijk}$  represents patient-specific baseline demographic, clinical, and socioeconomic factors,  $L_j$  are a series of binary variable for each Prisma clinic “j”,  $M_k$  is a count variable representing the number of months since the beginning the study that contains patient “i’s” index date, and  $C_{ijk}$  equals 1 if the episode occurred in a period in which the clinic “j” received or had previously received EIMG activation, 0 otherwise. The parameters  $\omega_j$ ,  $u_k$ , and  $\epsilon_{ijk}$  represent the model random effects associated with site “j”, month “k”, and patient “i”, respectively. We will estimate equation (1) using a generalized linear mixed model. The estimate of parameter  $\beta_4$  equals the effect of standardized EIMG training on the probability of the patient within the episode being referred to EIMG. Variables within  $X_{ijk}$  will include patient history of EIMG use. Our stepped wedge design will enable us to directly control for unmeasured factors associated with site and time. Secondary analyses will assess differences in the impact of standardized EIMG training by stratifying by eligible conditions (i.e., overweight/obese, hypertension, type 2 diabetes).

While EIMG activation will be randomly assigned to clinics using the stepped wedge design, actual EIMG referral decisions will remain at the discretion of provider and patient. As a result, referral decisions for some patients will be “non-compliant” at the clinical level. Providers may refer patients into EIMG based on factors unmeasured by the researcher that are related to study outcomes which can confound estimation of the effect of EIMG on study outcomes. With non-compliance, it is problematic to use “as treated” EIMG referral variation to assess the effects of EIMG referrals on study outcomes. Instrumental variable (IV) methods using randomized EIMG activation as an “instrument” will be used to avoid confounding problems. In this scenario IV estimation will yield consistent estimates of the effect of EIMG referral on study outcomes for the subset of patients whose referrals are responsive to the randomized clinical-level EIMG activation. This is known as the Complier Average Causal Effect (CACE). The CACE model is specified as:

$$(3) \quad Y_{ijk} = \alpha_0 + \alpha_1 \cdot X_{ijk} + \alpha_2 \cdot L_j + \alpha_3 \cdot M_k + \alpha_4 \cdot \hat{E}_{ijk} + \rho_j + \tau_k + \vartheta_{ijk}, \text{ where}$$

$\hat{E}_i$  equals the *predicted probability* of that patient “i” is referred to EIMG from equation (2); and the other variables defined as in equation (2). The parameters  $\rho_j$ ,  $\tau_k$ , and  $\vartheta_{ijk}$  represent the random effects associated with site “j”, month “k”, and patient “i”, respectively. The estimated parameter  $\alpha_4$  on  $\hat{E}_{ijk}$  is the CACE or the average treatment effect for patient subset whose EIMG referral was influenced by EIMG activation at the clinic.  $C_{ijk}$  in equation (2) serves as the “instrument” and only the portion of variation in  $\hat{E}_{ijk}$  stemming from  $C_{ijk}$  is used to estimate  $\alpha_4$ . Because  $C_{ijk}$  will be randomly assigned, EIMG referral variation stemming from this assignment will be independent of unmeasured confounding variables. Two-stage least squares (2SLS) IV estimators will be used to estimate the effects of EIMG referrals induced by clinical-level EIMG activation on study outcomes. For each study outcome, equation (2) will serve as the first stage

equation of 2SLS, and second stage model will be equation (3). Because our expected sample sizes will be greater than 500 *our 2SLS estimates will be distributed normally via the central limit theorem regardless of the distribution of the underlying error term.* Each 2SLS model will be estimated with robust standard error methods appropriate for 2SLS models using STATA to account for error structure in equation (3).

Define  $\alpha_{4C}$  as the 2SLS estimate when episode healthcare cost is the dependent variable in equation (3) and  $\alpha_{4H}$  as the 2SLS estimate when a health outcome change is the dependent variable in equation (3). Combining these estimates with the estimates of average patient EIMG training costs from Section F3.2 yields the following cost-effectiveness ratio of EIMG relative to standard care:

$$(4) \text{ EIMG Cost Effectiveness Ratio} = \left[ \frac{(\text{EIMG Training Costs per Patient} + \alpha_{4C})}{\alpha_{4H}} \right]$$

The ratio in equation (4) equals the incremental cost per patient associated with the EIMG referral induced by clinical-level EIMG activation per average change in health outcome associated with the EIMG referral induced by clinical-level EIMG activation. Separate estimates of equation (4) will be calculated by clinical diagnosis using the health outcome change in the denominator most relevant to the specific diagnosis (e.g., change in hemoglobin A1c for type 2 diabetes).

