## **12.5 Secondary Aim 2**

To evaluate, from the health system perspective, the cost of implementing EIMG, employing variation from the step-wedge design to estimate the effect of EIMG vs. standard care on costs and outcomes (effectiveness). These estimates will be used to obtain the incremental cost-effectiveness of EIMG vs. standard of care.

*Hypothesis 2: Patients receiving an EIMG referral and participating in the 12-week, community-based PA program will experience improved health outcomes, decreased healthcare service utilization, and a reduction in health care expenditures compared to patients that do not receive an EIMG referral and the opportunity to participate in the PA program.*

[figure not shown]

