**12.5.2 Episode of Care**

For each patient, a 90-day Run-in-Period prior to the index date will be used to calculate baseline patient baseline covariates. The EIMG Referral Decision Period is the 30 days after the index visit date. The Treatment Period is 120 days from the initial visit date, providing sufficient time for patient referral, entry into and completion of the 12-week PA program. The Outcome Period is the 90 days following the treatment period.

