**Figure 6. Defining the Episode of Care**

**12.5.3 Data Sources**

*Resource Activity Logs:* Prisma employment records by-labor-type (i.e., physician, nurse care coordinator, referral coordinator).

*Patient-Specific Healthcare Resources Used:* For EIMG-eligible patients, we will collect from the Prisma Health Epic EHR during the episode of care:

- 1) All healthcare utilization received by Healthcare Common Procedure Coding System (HCPCS), Diagnosis Related Group (DRG), and National Drug (NDC) codes; and
- 2) REDCap-based provider surveys to assess the resources used by EIMG and the 12-week PA program.

*Resource Unit Price Data:* Medicare standard pricing files for HCPCS, DRG and NDCs, and Prisma average wage rates of Prisma labor resources.

*Patient-Specific Health Outcomes:* From the Prisma Epic EHR we will collect: 1) blood pressure; 2) body weight; 3) hemoglobin A1c; 4) full lipid profiles, and 5) PA levels for each patient at the index visit and across the episode of care.

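### Aim 2 health change exists only for episodes with a measuring provider visit in days 121 to 210, while cost covers every eligible episode, so the health effect may be selected and equation (4) mixes two populations

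*Combined protocol and SAP*

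**What the plan says.** **Window.** Section 12.5.2: "The Treatment Period is 120 days from the initial visit date", and "The Outcome Period is the 90 days following the treatment period".

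**Health outcome.** Section 12.5.5 takes the change in blood pressure, body weight, hemoglobin A1c, lipids and physical activity between the index visit and "the first provider visit in the episode in the Outcome Period (Figure 6) in which this information is collected".

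**Cost outcome.** The same section defines episode cost as "the price-weighted sum of all healthcare resources used by patient" i during the episode. Section 12.5.3 gives the source population: "For EIMG-eligible patients, we will collect from the Prisma Health Epic EHR during the episode of care".

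**Hypothesis 2.** Section 12.5 predicts improved health together with "decreased healthcare service utilization, and a reduction in health care expenditures" for patients who are referred and take part.

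**Use of the two effects.** Section 12.5.5 fits a separate two-stage least squares (2SLS) model for each outcome. The cost effect α4C, plus training cost per patient, forms the numerator of equation (4), and the health effect α4H is the denominator. The only restriction stated for the ratio is by clinical diagnosis. Section 12.5 gives no method for missing health outcomes, no scheduled Outcome Period measurement, and no rule that the two models describe the same episodes.

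**The concern.** Two conditions must hold before an episode has a health outcome: the patient sees a provider in the Outcome Period, and the measure is taken at that visit. The second is likely to matter most for hemoglobin A1c and lipids. An episode that fails either condition has no value for the α4H model but remains in the α4C model.

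Returning for a visit is itself service use after the index date, and the plan expects EIMG to reduce service use. If referral changes who returns, and returning is related to how health has changed, then restricting the analysis to measured episodes conditions on something that treatment affects. An instrument does not cure this. Even if activation is treated as randomly assigned, as Section 12.5.5 assumes, the selection happens after assignment.

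The ratio has a further problem that needs no assumption about bias. Its numerator describes all eligible episodes and its denominator only the measured ones. Section 5.3 says that the economic evaluation may influence coverage and adoption decisions, so readers need to know which population the ratio describes.

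**Working it through.** The documents give no return rate, measurement rate, power or missing-data allowance for Aim 2, only an expected sample size above 500. There is no planned figure to reproduce.

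**Step 1: the window.** The Treatment Period ends on day 120. The Outcome Period runs from day 120 + 1 = 121 to day 120 + 90 = 210.

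**Step 2: who has a value.**

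| Quantity | Defined for | Needs a provider visit in days 121 to 210? |
|---|---|---|
| Episode cost (α4C) | every eligible episode | no |
| Health change (α4H) | episodes with a visit at which the measure is recorded | yes |

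**Step 3: illustration of the possible bias in α4H.** Inputs from the documents:
- SD of systolic change 15 mmHg and change of -7 mmHg, from the pilot patients referred for hypertension (Section 4.14). That change is uncontrolled, so using -7 as a true effect is an assumption.

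Assumed inputs:
- Mean change 0 without referral.
- 60% measured without referral; 50% or 40% measured with referral.
- Odds of being measured 1.5 or 2 times higher per SD worse change.
- Activation random, and no referral without activation.
- Complier share 0.03, chosen in view of the planned referral rate of up to 4% (Section 12.3).

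Let m0 and m1 be the mean changes among measured patients without and with referral, and let w be the share of measured patients in activated clinics who were referred. The instrumental-variable estimand is

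[w·m1 + (1 - w)·m0 - m0] / w = m1 - m0,

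so the complier share cancels. Numerical integration gives:

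| Measured, without / with referral | Odds ratio per SD | m0 | m1 | Estimate | Bias |
|---|---|---|---|---|---|
| 60% / 50% | 1.5 | 2.34 | -4.07 | -6.42 | +0.58 |
| 60% / 50% | 2 | 3.76 | -2.31 | -6.07 | +0.93 |
| 60% / 40% | 1.5 | 2.34 | -3.48 | -5.83 | +1.17 |
| 60% / 40% | 2 | 3.76 | -1.36 | -5.12 | +1.88 |
| 60% / 60% | 1.5 or 2 | 2.34 or 3.76 | -4.66 or -3.24 | -7.00 | 0 |
| any | 1 | 0 | -7.00 | -7.00 | 0 |

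**Step 4: check by hand.** Let G be the mean change of measured patients minus that of unmeasured patients, and let p0 and p1 be the shares measured without and with referral. If G is the same in both groups, bias = G × (p0 - p1). Without referral the overall mean is 0, so G = m0 / (1 - p0):
- Odds ratio 1.5: 2.34 / 0.4 = 5.85. Bias is 5.85 × 0.10 = 0.59 or 5.85 × 0.20 = 1.17.
- Odds ratio 2: 3.76 / 0.4 = 9.40. Bias is 9.40 × 0.10 = 0.94 or 9.40 × 0.20 = 1.88.

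These agree with the table to within 0.01. The formula shows that bias vanishes if G = 0 or p0 = p1, and that it changes sign if referral raises the share measured. It does not shrink with the true effect. A true -3 becomes -2.4 to -1.1 over the same four settings, and a true 0 becomes +0.6 to +1.9.

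**The case against.** **The size and direction are unknown.** Hypothesis 2 speaks of service use in general, not provider visits. EIMG also creates provider contact: a release form after a contraindication (Section 13.5) and physician evaluation after an emergency (Section 13.6). Section 3.2 notes that patients are often seen several times a year. All of this stands. Fewer visits is the natural reading of the hypothesis, but the documents do not establish it for days 121 to 210.

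**The plan may already collect what is needed.** Section 12.5.3 says that health outcomes will be collected for each patient at the index visit and across the episode. It schedules no measurement, however, and Section 12.5.5 narrows the analysed value to a provider visit. Measurements at the community facilities (Sections 9.3.1 and 12.4) exist only for patients who enroll, so they cannot fill the comparison side.

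**Weighting cannot remove selection on the change itself.** This is correct. In Step 3, weights that depend only on activation and referral leave m0 and m1 unchanged, so the estimate m1 - m0 does not move. Weights help to the extent that baseline values and covariates explain who is measured. A sensitivity analysis must cover the rest.

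**Matching the populations by dropping unmeasured episodes from the cost model would do harm.** This also stands. Cost needs no later visit, and avoided visits are among the savings that Hypothesis 2 would produce. The common population has to be all eligible episodes.

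**Conclusion.** The concern holds as a structural gap in a secondary aim. The visit-and-measurement condition, the cost definition for all eligible episodes, the absence of a missing-outcome method and the population mismatch in equation (4) follow from the text. The mismatch is there by definition. It changes the ratio to the extent that the health effect in measured episodes differs from that in all episodes.

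Bias in α4H is possible but not demonstrated. In the illustration it needs both an effect of referral on measurement and a link between measurement and health change. Under the assumed values it is +0.6 to +1.9 mmHg, so a true -7 is estimated as -6.4 to -5.1.

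Two stronger readings are tempting, and the documents support neither:
- A reader might infer that the health effect will certainly be understated. No visit or measurement rates are given, and the sign reverses if referral raises the share measured.
- A reader might infer that the ratio is wrong by the reciprocal of the share measured. That would require cost effects to arise only in patients who return, whereas under Hypothesis 2 some savings would come from patients not returning. It would also require zero training cost, because equation (4) adds training cost to α4C and that part would not rescale.

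**What to change.** Amend Section 12.5.5 as follows.

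1. **Outcome.** Define follow-up as the first value recorded in days 121 to 210 at any outpatient encounter or in any laboratory record, not only at a provider visit.
2. **Health model.** Fit α4H with inverse-probability-of-measurement weights based on baseline values and covariates, clinic, month, activation and referral, so that it targets all eligible episodes. State that this corrects only selection explained by those variables.
3. **Cost model.** Keep α4C on all eligible episodes, so that both parts of equation (4) target one population. Do not restrict cost to measured episodes.
4. **Reporting.** Give the share measured by referral status as well as by activation. At 3% to 4% referral, a fall of 10 to 20 points among referred patients moves the share by activation by only 0.03 × 10 = 0.3 to 0.04 × 20 = 0.8 points, so that comparison alone would be a weak check.
5. **Sensitivity.** Add a not-at-random (delta) analysis for α4H and the ratio, with unmeasured episodes differing from measured ones by a pre-stated range.

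This needs SAP wording, one model for the probability of measurement and the sensitivity runs. It uses EHR data and adds no patient visits. The costs are somewhat wider intervals, more measurement variation across encounter types and a little more analysis work.

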## 2.0 STUDY SYNOPSIS

Protocol Title	Implementing and Evaluating the Comprehensive Integration of Physical Activity into a Major Health System and Connecting Patients to Community-Based Physical Activity Programs
Principal Investigators	[name]; [name], MSPH
Study Sponsor	National Heart Lung and Blood Institute (NHLBI)
Study Design	Multiple case study trial examining the adoption, implementation, and reach of eligible patients visiting participating Prisma Health primary care clinics and receiving a referral to a 12-week evidence-informed physical activity (PA) program hosted at local community PA facilities.
Duration of Study Participation	
 
Prisma Health primary care clinics will have the opportunity to adopt Exercise is Medicine Greenville (EIMG)
 
Adopting clinics will be provided with an introductory video and have EIMG activated upon study entry (baseline)
 
After approximately three months, clinics will receive a more in-depth EIMG onboard training (months 0-3)
 
Clinic referral rates will be tracked for an additional six months after receiving the EIMG onboard training (months 4-9)
 
During the 9-month study period, eligible patients referred to participating community PA centers will have the option of enrolling in a 12-week, evidence-informed PA program
 

Summary of Investigational Intervention	
 
Implementation: our sequential design will test provider referral rates with eligible patients after: 1) an initial instructional video, and 2) more in-depth EIMG onboard training
 
Effectiveness: we will examine the effectiveness of a 12-week evidence-informed physical activity (PA) on patient PA levels and health outcomes
 

Summary of Key Eligibility Criteria	
 
Prisma Health primary care clinics not yet onboarded to EIMG
 
Clinic managers at all Prisma Health primary care clinics eligible for the study (adoption)
 
Healthcare providers at the Prisma Health primary care clinics that chose to adopt EIMG (implementation)
 
Patients, age 18 or older, attending participating Prisma Health primary care clinics for whom exercise is not contraindicated (effectiveness)
 

Primary Outcome Measure	
 
Referral rates of eligible patients to the evidence-informed PA program
 

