### 5.2 Secondary Objectives

*Secondary Aim 1.* To assess the effectiveness of participating in the evidence-informed, 12-week PA program at the community PA facilities on patient health outcomes (i.e., body weight, blood pressure, hemoglobin A1c, lipid profiles) captured in their electronic health records.

*Secondary Aim 2.* To evaluate, from a health system perspective, the cost of implementing EIMG to estimate the effort of EIMG vs. standard care on costs and outcomes (effectiveness). We will use these estimates to obtain the incremental cost-effectiveness of EIMG vs. standard of care.

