### **6.2.7 Rationale for Control Condition**

The selection of our control group was influenced by several factors. There are currently only 20 Prisma Health primary care clinics that have not received EIMG onboarding and activation and that are within 15 miles or less of a participating community PA facility. There are no other equivalent Prisma Health primary care clinics to serve as matched controls (i.e., via a stepped wedge design). We are then left with two groups of clinics to serve as controls. The first of these is using a within-clinic design and comparing patient health outcomes before and after the dissemination of the initial EIMG Instructional Video. Secondly, from past experiences, we anticipate that several of the 20 clinics will choose not to adopt EIMG and/or will be non-responsive to our invitation. As one of our study aims, we will evaluate contextual factors and differences between adopting and non-adopting clinics. Clinics that do not adopt EIMG will not be 'activated' and can therefore serve as control clinics, particularly when evaluating patient-level outcomes, as none of their patients will have had the opportunity to participate in EIMG.

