### 10.0 STUDY TIMELINE

This study will be conducted over three phases: 1) EIMG Adoption; 2) EIMG Introductory Video; and 3) EIMG Onboarding Training. *Phase I* will occur over the first month of this project in which practice managers and their clinic will be offered the opportunity to adopt EIMG, No research activities will take place during this phase. *Phase II* will occur between months 2 through 5, beginning with the dissemination of the EIMG Introductory Video to practice managers and EIMG activation at adopting clinics. This phase will involve several study activities including conducting individual (adoption) interviews with practice managers, clinic staff completing the online ORCA questionnaire, and conducting individual interviews with patients receiving an EIMG referral. *Phase III* will occur from months 6 through 9, beginning with the EIMG onboard training. This phase will involve clinic staff completing the online ORCA questionnaire, conducting individual (implementation) interviews with clinic staff, and continuing the individual interviews with patients receiving an EIMG referral.

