#### 10.1 Timetable - Clinic Assessment of EIMG Referral Pathway

		Month								
	Estimated Time	1	2	3	4	5	6	7	8	9
Practice Manager Assessments										
Individual Interviews (Adoption)	20		X							
Clinic Staff Assessments										
ORCA Questionnaire	10			X	X			X	X	
Individual Interviews (Implementation)	20							X	X	X
Patient Assessments										
Individual Interviews (Enrollment)	30		X	X	X	X	X	X	X	X
EHR Patient Information Extraction	n/a		X	X	X	X	X	X	X	X

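### Secondary Aim 2: equations (2) and (3) rely on randomised stepped activation that the current design lacks, and do not implement the standard-care comparators named in section 6

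*Combined protocol and SAP*

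**What the plan says.** Section 5.2 sets Secondary Aim 2 "to estimate the effort of EIMG vs. standard care on costs and outcomes", and equation (4) in 12.5.5 is a cost-effectiveness ratio relative to standard care.

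The model in 12.5.5 has three relevant parts:
- Clinic terms L_j, which "are a series of binary variable for each Prisma clinic".
- A time term M_k, which "is a count variable representing the number of months since the beginning the study".
- An exposure C, equal to 1 when the clinic "received or had previously received EIMG activation, 0 otherwise". The same section also describes the exposure, and beta_4, in terms of standardised training.

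C is the instrument for referral. Sections 12.5 and 12.5.5 justify it by saying that activation is randomly assigned under a stepped wedge.

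The design sections differ. Section 6.1 describes a single-arm study. Section 8.1 invites all clinics at once and rules out a stepped approach. Section 6.2.7 says no further equivalent clinics exist for one. On timing, 2.0 says adopting clinics will "have EIMG activated upon study entry (baseline", while 10.0 starts Phase II in month 2, "beginning with the dissemination of the EIMG Introductory Video to practice managers and EIMG activation at adopting clinics".

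Comparators are named outside 12.5. Section 6.1 compares referred patients with matched patients at non-adopting clinics, on outcomes and costs. Section 6.2.7 gives a within-clinic control, "comparing patient health outcomes before and after the dissemination of the initial EIMG Instructional Video", and adds non-adopting clinics as a second control.

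**The concern.** An indicator for every clinic removes any constant difference between adopting and non-adopting clinics. What remains to identify C is change over time within adopting clinics. A stepped wedge would supply that, because clinics would wait different lengths of time under standard care. Here every adopting clinic is activated together, at or near the start of the time axis. Non-adopting clinics then inform only the time trend and the patient-covariate coefficients.

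At stake are beta_4, both versions of alpha_4 (cost and health outcome), and the ratio in equation (4). In the worst case they cannot be estimated. In the better case they lean on a thin and largely exposed control period, while the text describes the instrument as randomised.

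**Working it through.** Section 12.5 states no power or precision figure for this aim (only an expected sample size above 500), so there is none to reproduce. The check is whether C varies once clinic and time are in the model.

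**Inputs.** 20 clinics are offered EIMG (7.1), in one wave (8.1). There are p pre-activation months and q post-activation months. Activation at study entry gives p = 0 (2.0). Activation at the start of month 2, with data through month 9, gives p = 1 and q = 8 (10.0). An episode runs 120 + 90 = 210 days (12.5.2). The number adopting is not given, so I assume n_A = 5, 10, 15 or 20, with n_N = 20 − n_A. I also assume equal episodes per clinic-month.

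**Formulas.** RSS is the residual sum of squares of C after clinic indicators and time, in clinic-month units. The standard error of beta_4 is proportional to 1/√RSS, and RSS = 0 means C is not identified. With T = p + q:
- Month effects: RSS = [n_A·n_N/20] × [pq/T]
- Linear month: RSS = n_A·pq/T − (n_A·pq/2)² / (20·S), where S = T(T² − 1)/12

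**Step 1, no pre-activation month.** With p = 0, RSS = 0 for every split. C equals the sum of the adopting clinics' indicators. With linear time the 20 clinic indicators, month and C make 22 columns of rank 21. The random site term does not help, because the clinic indicators already span it.

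**Step 2, month 1 only (p = 1, q = 8, T = 9, S = 60), 10/10 split.**
- Linear month: 10 × 8/9 − (10 × 4)²/(20 × 60) = 8.89 − 1.33 = 7.56
- Month effects: 5 × 8/9 = 4.44

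| Adopting/non-adopting | Linear month | Month effects |
|---|---|---|
| 5/15 | 4.11 | 3.33 |
| 10/10 | 7.56 | 4.44 |
| 15/5 | 10.33 | 3.33 |
| 20/0 | 12.44 | 0 |

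At 10/10, clinic and time explain 83% (linear month) or 90% (month effects) of the variation in C.

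**Step 3, exposure within month-1 episodes.** Take 30-day months and activation on day 31. An index visit on day 1 has 180 of its 210 episode days on or after activation (86%). One on day 30 has 209 of 210 (99.5%). Of the 30-day referral decision period, 0 to 29 days also fall there.

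**Step 4, C read as standardised training.** This gives four months before and four after (p = q = 4, T = 8, S = 42). At 10/10:
- Linear month: 10 × 16/8 − (10 × 8)²/(20 × 42) = 20 − 7.62 = 12.38
- Month effects: 5 × 16/8 = 10.00

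C is identified, but at adopting clinics its zero state is the video phase with referral already active. The contrast is training against video, not EIMG against standard care.

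**The case against.** The strongest defence is that the protocol does plan a standard-care comparison. Sections 6.1 and 6.2.7 name matched patients at non-adopting clinics and a before-versus-after-video control. Section 6.1 also promises EHR data from before and after onboarding. Sections 6.2.7 and 7.1 speak of onboarding together with activation as joining EIMG, so a pre-activation pull may well be intended. The 90-day run-in in 12.5.2 needs data from before each index visit in any case. All of this stands. A reader might infer that the plan has no standard-care comparator, and the documents do not support that. What is missing is the link: 12.5 never brings these comparators into the equations, gives no window length, and leaves the term study period in 12.5.1 undefined.

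Four further inferences go too far:
- That C is always collinear with clinic. This is exact only with no pre-activation month, or with month effects and no non-adopting clinic.
- That the estimates rest on a single month of data. Only the pre-activation side is that thin; up to eight months follow activation.
- That the data begin in month 2, because the row "EHR Patient Information Extraction" in 10.1 is first marked there. That table schedules activities, and 7.2 and 7.4 describe retrospective extraction.
- That software would print a raw adopter-versus-non-adopter difference. The output depends on which column is dropped: if C goes there is no coefficient, and if clinic indicators go the contrast depends on which ones.

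**Conclusion.** Wrong as written. The randomised, stepped variation that 12.5 relies on is not in the current design, and equations (2) and (3) do not carry the comparators named in 6.1 and 6.2.7.

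The size depends on a timeline that the documents leave open. If activation coincides with study start, alpha_4 and the cost-effectiveness ratio are not estimable at any adoption split. If month 1 precedes activation, they are estimable but weakly supported, and the adopting clinics' control episodes lie almost wholly after activation. If C means training, the model estimates a different contrast.

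The figures assume equal episodes per clinic-month and the stated splits. The result for no pre-activation month does not depend on either. The primary referral analysis and Secondary Aim 1 are untouched.

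**What to change.** In 12.5:
1. Delete the stepped-wedge and random-assignment statements.
2. Define C once, as activation, for the EIMG-versus-standard-care contrast.
3. Define a pre-activation index-visit window at all 20 offered clinics, with every 210-day episode closing before activation. One example is 12 months of index visits ending 210 days before activation, plus the 90-day run-in. The EHR query would then reach back about 365 + 210 + 90 = 665 days before activation.
4. Set C = 0 throughout that window and start M_k at its beginning. Reconcile the activation date between 2.0 and 10.0.
5. Fit clinic and month effects, so that alpha_4 rests on the within-clinic change at adopting clinics relative to the change at non-adopting clinics.
6. State that adoption is self-selected, so the estimate rests on parallel trends and is not a complier effect from a randomised instrument.

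As an illustration, this window with eight post-activation months and a 10/10 split gives RSS = 5 × (12 × 8)/20 = 24.0 with month effects, against 4.44 with month 1 alone. The 12 months are my choice and do not come from the documents. The contrast needs at least one non-adopting clinic; 6.2.7 expects several.

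The cost is wording and a longer look-back in the same retrospective query, with no new patients or visits. The downside is a weaker causal claim than the text now makes.
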